#### **Development of the Game and Intervention**

During the preintervention period, regular focus groups comprising in-house participants, computer programmers, and exercise scientists with specialisms in delivering HIT were held. Together, we explored opportunities to gamify HIT protocols. Boxing was an obvious theme for gamification as it involves high-intensity exercise, and the subculture already exists within the target population of lower working-class males of the North-East of England. The complete set of hardware used in the trials comprised a single computer with a dedicated graphics card (GeForce GTX 960), two standard 23-inch monitors, two Kinect for Windows sensors, four wrist-mounted wireless inertial measurement units (developed in-house to reduce latency in the Kinect datastream), and two wireless chest-worn heart-rate monitors (Polar RS400, Polar Electro Oy, Kempele, Finland). In addition, participants wore boxing-specific resistance bands (ShadowBoxer Pty, Australia) to increase levels of exertion and reduce eccentric muscle contractions during the deceleration phase of punching. The movement data from the sensors were streamed to a gaming engine via a User Datagram Protocol with a latency of approximately 15 ms. Input from the skeletal tracking module of the Kinect system and inertial measurement units were converted to a digital avatar using purpose-written functions to convert each body segment long-axis (19 in total) into threedimensional quaternions. The C# programming language was used throughout to create scripts for gameplay.

Commercial games are primarily designed for entertainment and recreation for younger populations and tend to have colorful and visually busy game and user interfaces. Furthermore, commercially available games are mostly designed for enjoyment and not based on basic exercise principles. For games to promote beneficial changes in health, they need to engage physiological systems in a meaningful manner that is relevant for the function being trained. Our philosophy was to ensure that the gameplay was simple and, where possible, true to the rules of boxing. Each avatar was assigned collision objects with inertial characteristics on the trunk, head, and hands, thus enabling the physics engine to superimpose realistic joint movements in response to being hit. As in real boxing, the primary mechanism for scoring was to successfully land a punch on either the trunk or head of the opponent. The number of points awarded per punch was the product of the current heart rate (expressed as a percentage of maximal) and speed of impact (ms). Thus, for example, a punch landing to the head with a relative speed of 9 ms and at 95% of maximal heart rate (ie, 95% HRmax) was awarded 8.55 points (ie, 9 x 0.95). Each participant was provided with biofeedback in the form of a partial arc positioned around the opponent's head; the angle subtended by this arc was linked to the current heart rate.

For example, when player 1 was working at 50% of maximal heart rate, an arc of 180° was displayed around the head of player 2. The players were made aware that the angle of the arc was proportional to their current training intensity, which in turn contributed strongly to punch power and points scoring. They were also aware that large global displacements of their center of mass (eg, bouncing up and down) would increase this intensity but with a lag of approximately 20 to 30s. This arc was visible in their monitor only and was active throughout the exergaming session (ie, during both repetitions and rest), essentially allowing the participants to self-regulate training intensity per the oncoming requirements of the game. Although we kept on-screen text to a minimum, we elected to display a countdown timer during some periods. These were during the final 30 s of active recovery to encourage the elevation of training intensity in preparation for a repetition and during the latter 10 s of each repetition to encourage all-out punching right up until the bell. Following preliminary tests, we removed the ability to block punches as this was observed to be energetically undemanding; thus, the only forms of defense were to attack before being hit or to dodge the oncoming punch using whole body movements. For similar reasons, we limited the periods of allowable close-up punching. Specifically, after 1 s of close-up punching, the referee interrupted the fight and ordered both participants to race back to their respective corners (ie, 3 m

backwards of backwards stepping). The winner of each mini race received an additional 50 points; equivalent to approximately 6 to 7 well-timed punches. After several iterations of observing kinematics, heart rates, and tactics during gameplay, we prepared the exergaming system (ie, both hardware and software) for use in the target settings.

## Participants

We conducted a 6-week exploratory controlled trial designed to assess the fidelity of the game in terms of delivering the intended training stimulus and to examine the effect of the intervention on selected health outcomes. As appropriate for an exploratory trial, we did not conduct formal sample size estimation a priori, rather the CIs would be used to inform future trials. Men are commonly referred to as a hard-to-reach population to engage in health promotion activities, where a targeted recruitment approach at locations predominantly attended by men may facilitate uptake of participants. Therefore, to maximize recruitment within our intended population, relevant gatekeepers were approached at institutions positioned within regions of social deprivation. Thus, two settings used for recruitment and the trials were a social club and mosque, both situated within deprived regions of Middlesbrough, United Kingdom (TS1 and TS4). Recruitment in the social club relied heavily on the gatekeeper (club secretary), whereas uptake of South Asian men from a local mosque was more straightforward; all 9 mosque participants were recruited from a single demonstration (and we had similar experiences in previous iterations). Presumably, the intervention was culturally salient in this population; the North of England has developed some famous prominent Muslim boxers (eg, Amir Kahn and Naseem Hamed) in recent years, and when delivered in the safe form, was acceptable to the respected leaders of the religious groups (ie, the Imam of the mosque). A total of 24 males were recruited into the trial using relevant gatekeepers at institutions positioned within regions of social deprivation. Two recruitment drives (October 2014 and February 2015) took place, and these involved live demonstrations of the technology followed by word-ofmouth and snowballing approaches. The exergaming system was important in this recruitment process because it provided something tangible and interesting to engage potential participants.

Inclusion criteria were deliberately broad to maximize recruitment, that is, apparently healthy, as defined by ACSM guidelines and in the age range of 18 to 55 years. Participants were given a £15 shopping voucher upon completion of follow-up measures (week 7) irrespective of their adherence to the intervention protocol or group allocation. The intervention took place from November 2014 to December 2014 (social club) and March 2015 to April 2015 (mosque). Postcode data were analyzed to match against indices of multiple deprivation in lower-layer super output areas to check whether the cohort fell within our target population.

A third-party minimization process using baseline measures of age, waist circumference, and predicted maximum oxygen consumption  $(VO_2 \text{ max})$  was used to remove bias in group allocation. The control group was instructed to maintain their current physical activity levels and inform the researchers should any changes arise during the intervention

To explore perceptions of the exergame and the HIT regime, semistructured interviews were conducted with 5 intervention participants following the 6-week training period, which were analyzed semantically. The study was approved by the ethics committee of Teesside University, United Kingdom, and written informed consent was obtained from all participants.

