These percent chances were qualified via probabilistic terms assigned using the following scale: 25 to 75%, possibly; 75 to 95%, likely; 95 to 99.5%, very likely; and >99.5%, most likely. To determine the magnitude of the within-participant variability in our training heart rate and RPE, the values were doubled and then interpreted against aforementioned MPID. All training data effects were evaluated mechanistically, whereby if the 90% CL overlapped the thresholds for the smallest worthwhile positive and negative effects, the effect was deemed unclear. The effect of HIT on our outcome measures was determined using a custom-made spreadsheet, with the baseline value of the dependent variable used as a covariate to control for baseline between-group imbalances. Following this, standardized thresholds for small, moderate, and large changes (0.2, 0.6, and 1.2, respectively) derived from between-subject SDs of the baseline values were used to assess the magnitude of all effects, with magnitude-based inferences subsequently applied. Here, all inferences were categorized as clinical, with the default probabilities for declaring an effect clinically beneficial being <0.5% (most unlikely) for harm and >25% (possibly) for benefit.

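### Setting coincides with calendar period and recruitment route, but is neither a named minimization factor nor a term in the outcome model

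*Combined protocol and SAP*

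**What the plan says.** **Allocation (Participants).** The method is "A third-party minimization process using baseline measures of age, waist circumference, and predicted maximum oxygen consumption". No stratification or separate allocation by setting is described. The allocation ratio and any random element are not given. Nor is it stated whether one set of minimization tallies served both settings.

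**Settings (Participants).** The "two settings used for recruitment and the trials were a social club and mosque". On timing: "The intervention took place from November 2014 to December 2014 (social club) and March 2015 to April 2015 (mosque"). Also, "Two recruitment drives (October 2014 and February 2015) took place". On numbers, "A total of 24 males were recruited into the trial", and "all 9 mosque participants were recruited from a single demonstration". That leaves 24 − 9 = 15 for the club, if every man came from one of the two settings. Club recruitment depended mainly on the club secretary as gatekeeper, whereas "uptake of South Asian men from a local mosque was more straightforward".

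**Analysis (Statistical Analysis).** The effect on outcomes is estimated in a custom-made spreadsheet "with the baseline value of the dependent variable used as a covariate". No other covariate is named. Effects are judged against standardized thresholds, the smallest being 0.2 baseline SD.

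**The concern.** Setting here is more than a site label. It fixes the calendar period, since the two periods do not overlap, and it goes with a different recruitment route. It was known for every man before allocation, so it could have been balanced.

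Adjusting for the outcome's baseline deals with different starting values. It does not remove a difference between settings in how much men change over six weeks, for example from season. If one arm holds more mosque men than the other, part of that difference is read as an intervention effect. With 24 men, a few men placed unevenly are enough to matter. The Participants section intends the confidence intervals to inform future trials, so a shifted estimate would be carried forward.

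**Working it through.** The plan gives no imbalance or power figure, so there is nothing of its own to reproduce.

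**Inputs from the documents:** 24 men; 9 from the mosque, hence 15 from the club by subtraction; three minimization factors; smallest effect threshold 0.2 SD.

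**Assumptions:** arms of 12:12, and a setting difference in 6-week change of 0.2 to 0.8 baseline SD. The documents give neither.

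**Step 1. Allocation unrelated to setting.** The number of mosque men in one arm is hypergeometric: P(k) = C(9,k) × C(15,12−k) / C(24,12), with C(24,12) = 2,704,156.

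- k = 6: 84 × 5,005 = 420,420
- k = 7: 36 × 3,003 = 108,108
- k = 8: 9 × 1,365 = 12,285
- k = 9: 1 × 455 = 455

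Counting both directions:

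- 6:3 or worse: 2 × 541,268 / 2,704,156 = 40.0%
- 7:2 or worse: 2 × 120,848 / 2,704,156 = 8.9%

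For arms of 13:11 and 14:10 the 6:3-or-worse figures are 42.3% and 48.6%. With unequal arms, however, such a split does not always mean a large gap in mosque share. The chance of a gap of at least 25 percentage points is 40% at 12:12 and about 21% at 13:11 or 14:10.

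**Step 2. Allocation in two successive blocks.** The club intervention ended in December 2014, before the February 2015 drive, so the club men must have been allocated first. Minimization was simulated on three two-level factors, 15 club men then 9 mosque men, 6,000 runs per scenario. The ranges cover mosque men having the same factor distribution as club men, or one shifted by 0.5 SD. Chance of a 6:3 or worse mosque split:

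| Tallies | Probability of preferred arm | Setting not a factor | Setting added as a factor |
|---|---|---|---|
| Carried over | 1.0 | 6.3–6.8% | 0.2% |
| Carried over | 0.8 | 26.0–27.8% | 13.9–15.2% |
| Restarted at mosque | 1.0 | below 0.1% | 0% |
| Restarted at mosque | 0.8 | 10.0–10.3% | 7.2–7.7% |

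Without setting as a factor, 7:2 or worse occurred in at most 3.8% of runs.

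**Step 3. Effect on the estimate.** Shift = (mosque share in one arm − mosque share in the other) × setting difference in change.

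- 6:3 split: 6/12 − 3/12 = 0.25. Shift: 0.25 × 0.2 = 0.05 SD to 0.25 × 0.8 = 0.20 SD.
- 7:2 split: 7/12 − 2/12 = 0.417. Shift: 0.08 to 0.33 SD.

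The shift reaches 0.2 SD when the setting difference is 0.2/0.25 = 0.8 SD (6:3) or 0.2/0.417 = 0.48 SD (7:2).

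**The case against.** The strongest reply is that the gap may be one of reporting only. Separate minimization in each setting on the three named factors fits the text fully, and would leave setting nearly balanced if assignment was close to deterministic. This stands. It is why the 40% is an upper guide and why confidence is medium.

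Second, the imbalance is a matter of chance. Either arm is equally likely to hold the excess, so the expected bias is zero. This also stands: the point concerns the one allocation realized, and no systematic bias is shown.

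Third, the shift is modest beside the trial's imprecision. With 12 per arm and a residual SD equal to the baseline SD (an assumption), the 90% half-width is about 1.645 × √(2/12) = 0.67 SD. That lowers the severity. It does not justify leaving out a cheap safeguard, because effects are judged against a 0.2 SD threshold.

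Fourth, no setting or seasonal effect is documented. An effect of 0.8 SD from setting alone would exceed the plan's own threshold for a moderate change (0.6 SD), so the upper end of the assumed range is demanding.

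A reader might also infer that one setting could be left almost without controls. The documents do not support this. At 12:12 the club has at least 12 − 9 = 3 men in each arm. The mosque has 0 or 1 controls with probability (455 + 12,285) / 2,704,156 = 0.5%, even when allocation ignores setting.

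**Conclusion.** The point holds as a risk that the plan leaves open. Setting is handled neither among the named minimization factors nor in the outcome model. The chance of a 6:3 or worse mosque split lies between about 0 and 28% under two-block minimization, depending on details the plan does not state, with 40% as the upper guide. Such a split would move the group difference by 0.05 to 0.20 SD, given 12:12 arms and an assumed setting difference of 0.2 to 0.8 SD. Severity is minor to moderate for an exploratory trial of 24; confidence is medium.

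Two stronger readings should be avoided. The text reviewed gives no arm-by-setting counts, so it does not show that the arms were in fact imbalanced. Nor does it establish that the settings differ in ethnicity: the mosque recruits are described as South Asian, but the ethnicity of the club men is not stated.

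**What to change.** 1. Run the minimization within setting, or add setting as a factor. State the allocation ratio, the probability of assigning the preferred arm, and whether tallies carried over or restarted.
2. Report the arm-by-setting counts.
3. Enter setting as a fixed effect in the baseline-adjusted outcome analysis, at least as a sensitivity analysis. This remains possible after allocation. It is useful even with setting as a factor: with carried-over tallies and a preferred-arm probability of 0.8, a 14 to 15% chance of a 6:3 or worse split remains.

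**Cost.** One more factor for the third party. In the analysis, 1 degree of freedom: with 24 men, residual df fall from 24 − 3 = 21 to 20, and the 90% t value rises from 1.721 to 1.725. If the split were 6:3, the squared correlation between arm and setting would be (6×9 − 3×6)² / (9×15×12×12) = 1,296/19,440 = 0.067. The standard error would then grow by a factor of 1/√(1 − 0.067) = 1.035, before any gain from lower residual variance. The analysis tool must also accept a second covariate, and the documents do not say whether the spreadsheet does.

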## Measures

All measures were assessed pre and post intervention. Blood pressure was collected on the left arm positioned at heart height with the subjects in a seated position by an automatic upper arm blood pressure monitor (Omron MX13). Measures were made at least three times at 3-min intervals,

where an average of the two lowest measures was used for analysis. Waist circumference was measured using the World Health Organization guidelines. Predicted VO2 max was obtained by performing a submaximal 8-min ramped step test. Heart rate response (Polar T34; PolarElectro OY, Kempele, Finland) and simultaneous breath-by-breath expired gas were collected using a portable indirect calorimeter (Cosmed K4 b2; Rome, Italy), calibrated per the manufacturer's guidelines. Individual HRmax was estimated and plotted against VO2 data for the determination of predicted VO2 max.

## **Intervention Delivery**

Evidence recommends a minimum duration of 12 weeks for a HIT protocol to promote favorable changes in blood pressure and anthropometric measurements of obesity. However, a 6-week intervention was selected, as a minimum of 13 sessions (0.16 work/rest ratio) is sufficient to elicit moderate improvements in VO2 max in sedentary individuals. Additionally, there is still ambiguity regarding the optimal work-to-rest ratio when designing HIT interventions, particularly in populations with varied age, baseline fitness, and training experience. Therefore, longer duration HIT models (1-4 min) were deemed unsuitable for our target population. Furthermore, minigames (such as the current exergame) have short life spans, where adherence to a longer intervention (eg, 12 weeks) may diminish over time and influence health outcomes. This was evident from a 12-week pilot study (unpublished data) using an exergame in the same population that saw attendance drop from 53% during week 2 to 16% during week 12.

Participants allocated to the intervention group were invited to attend three sessions of exergaming per week. At the beginning of the exergaming session, participants were required to complete a 6-min structured warm-up consisting of a series of exercises on a 210 mm step until both participants reached ~70% HRmax. Session workloads with volumetric progression were set automatically once the user's identifying information was entered. The session workloads were 120s-, 150-s, and 180-s of work during weeks 1 and 2, weeks 3 and 4, and weeks 5 and 6, respectively.

To avoid staleness, the repetition lengths (10, 20, or 30-s) were randomly selected at the beginning of each round. We set the work-to-rest ratio at 1:4, and thus, the respective repetitions were followed by 40, 80, or 120-s of active recovery. Participants were instructed to perform the repetitions at an intensity  $\geq$ 85% HRmax. Each exergaming session took approximately 30 to 40 min to complete, including equipment set-up, warm-up with additional enjoyment, and task immersion questionnaires upon completion of the HIT bouts (not reported here). Heart rate responses were taken within repetitions and therefore, did not include any of the recovery period. This, therefore, avoided an overestimation of physiological load, which can occur when heart rate continues to rise after exercise cessation.

### **Statistical Analysis**

Exergaming session attendance was calculated using descriptive statistics. Training data (heart rate [repetition mean and peak], rating of perceived exertion [RPE]) were analyzed using a mixed linear model with a random intercept (Statistical Package for the Social Sciences [SPSS] version 23 [IBM Corp]).

This approach enabled us to calculate (1) the within-participant variability in the training dose, expressed as an SD; (2) the effect of HIT repetition duration (entered as a fixed effect) on heart rate and RPE; and (3) the change in heart rate and RPE across the 6-week HIT intervention, with session number (1-18) entered as a fixed effect. A priori, we defined a minimal practically important difference (MPID) in training heart rates as two percentage points, given that when training at high-intensity, this difference influences the adaptive response.

The MPID for RPE was set at one arbitrary unit (AU) on the Borg CR10 Scale, representing a full increment change on the scale. Inferences were then based on the disposition of the 90% confidence limits (CLs) for the mean difference to these MPID; the probability (percent chances) that differences in heart rate and RPE between HIT repetitions of different durations or across the 6-week intervention were substantial (>2 percentage points, >1 AU) or trivial was calculated as per the magnitude-based inference approach described by Batterham and Hopkins, an approach that has been advocated within user research.

These percent chances were qualified via probabilistic terms assigned using the following scale: 25 to 75%, possibly; 75 to 95%, likely; 95 to 99.5%, very likely; and >99.5%, most likely. To determine the magnitude of the within-participant variability in our training heart rate and RPE, the values were doubled and then interpreted against aforementioned MPID. All training data effects were evaluated mechanistically, whereby if the 90% CL overlapped the thresholds for the smallest worthwhile positive and negative effects, the effect was deemed unclear. The effect of HIT on our outcome measures was determined using a custom-made spreadsheet, with the baseline value of the dependent variable used as a covariate to control for baseline between-group imbalances. Following this, standardized thresholds for small, moderate, and large changes (0.2, 0.6, and 1.2, respectively) derived from between-subject SDs of the baseline values were used to assess the magnitude of all effects, with magnitude-based inferences subsequently applied. Here, all inferences were categorized as clinical, with the default probabilities for declaring an effect clinically beneficial being <0.5% (most unlikely) for harm and >25% (possibly) for benefit.

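### The training-data model has no term for the two opponents in a bout or for session, so its 90% limits for the duration and session effects are miscalibrated unless those dependences are absent.

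*Combined protocol and SAP*

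**What the plan says.** Statistical Analysis says that the training data (mean and peak heart rate per repetition, and RPE) "were analyzed using a mixed linear model with a random intercept". Repetition duration and session number (1 to 18) are fixed effects. The grouping unit of the intercept is not named. One stated aim is to estimate "the within-participant variability in the training dose, expressed as an SD", which points to participant. No pair, bout or session random term, random slope or correlated residual is described. Differences by duration and across sessions are judged by where the 90% limits lie against the MPID (2 percentage points for heart rate, 1 unit for RPE) and by percent chances labelled *possibly*, *likely*, *very likely* and so on.

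The game is for two players. Under Development of the Game and Intervention, the hardware includes "two standard 23-inch monitors, two Kinect for Windows sensors" and two heart-rate monitors. On scoring: "As in real boxing, the primary mechanism for scoring was to successfully land a punch on either the trunk or head of the opponent". After 1 s of close-up punching, "the referee interrupted the fight and ordered both participants to race back to their respective corners". Blocking was removed, which leaves only attacking first or dodging as defence. Under Intervention Delivery, the warm-up runs "until both participants reached ~70% HRmax", and a length of 10, 20 or 30 s is drawn at random at the start of each round.

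**The concern.** One man's exertion in a repetition is partly a response to his opponent's, and both race at each referee break. Two men fighting the same round presumably also share its repetition length, although the documents do not say so outright. Duration is then a property of the bout and not of the man. A participant intercept removes stable differences between men, but leaves two opponents in the same repetition conditionally independent.

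Session number raises a related problem. All of a man's repetitions in one session share that day's form, and men may differ in how they change over 18 sessions. With one random intercept, every repetition counts as a separate piece of evidence about the session trend.

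The SE feeds directly into the limits and percent chances, so a miscalibrated SE can move an effect between *unclear*, *likely* and *very likely* without any change in the data. The verdict on within-participant variability is not affected in this way: it compares a doubled SD with the MPID and uses no limits.

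**Working it through.** The plan states no sample size, power or limit width, so there is no figure of its own to reproduce.

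**Inputs from the documents:** 90% limits (z = 1.645); lengths of 10, 20 or 30 s; session work of 120, 150 and 180 s (about 6, 7.5 and 9 repetitions at a mean of 20 s); 18 sessions; 24 men in total, arm sizes not given.

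**Assumptions:** opponents share each round's length; rho is their residual correlation within a repetition. For the simulation: 12 players in 6 fixed pairs, 80% of pair sessions held, between-player SD 4 and repetition SD 4 percentage points.

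**1. Pairing and the duration effect.** With a shared length, the information comes from pair means. Their residual variance is σ²(1 + rho)/2, while the described model takes σ²/2. Hence

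- true SE / reported SE = √(1 + rho)
- actual coverage = 2Φ(1.645/√(1 + rho)) − 1

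| rho (assumed) | SE ratio | Coverage of nominal 90% |
|---|---|---|
| −0.3 | √0.7 = 0.84 | 95.1% |
| 0 | 1.00 | 90.0% |
| 0.1 | √1.1 = 1.05 | 88.3% |
| 0.3 | √1.3 = 1.14 | 85.1% |
| 0.5 | √1.5 = 1.22 | 82.1% |

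The ratio cannot exceed √2 = 1.41. If lengths were instead drawn separately for each man, this inflation of the duration SE would largely vanish.

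**2. Simulation of the participant random-intercept model** (300 runs per row; Monte Carlo error about 2 points near 90%, about 3 at the lowest values).

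| Dependence added | Duration coverage | Session coverage |
|---|---|---|
| None | 92.7% | 87.7% |
| rho 0.3 | 84.7% | 84.7% |
| rho 0.5 | 83.3% | 83.7% |
| rho −0.3 | 96.0% | 96.0% |
| Participant-by-session SD 2 points, independent | 89.3% | 70.3% |
| Same, opponents' session effects correlated 0.5 | 90.0% | 61.3% |
| Between-player SD 2 points in the session 1-to-18 change | 87.0% | 63.7% |

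A hand check of the last row: the model's mean SE was 0.364 points. Twelve players whose changes have SD 2 add variance 2²/12 = 0.333, so the true SE is about √(0.364² + 0.333) = √0.466 = 0.68. The ratio is 0.68/0.364 = 1.87, and 2Φ(1.645/1.87) − 1 is about 62%, in line with the simulated 63.7%.

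**3. Does respecting the pairing repair it?** Analysis at pair level, with 1500 runs and fixed participant intercepts as the comparator:

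| Scenario | Duration, before → after | Session, before → after |
|---|---|---|
| rho 0.3 | 85.3% → 90.2% | 84.6% → 89.5% |
| rho 0.5 | 81.8% → 89.7% | 83.3% → 90.1% |
| Participant-by-session SD 2, independent | not affected | 71.1% → 90.3% |

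In the last row the mean session SE rises from 0.40 to 0.62 points. The repair was not simulated for random slopes or for session effects shared by opponents.

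**4. Effect on a label (assumed figures).** A 3-point difference with reported SE 0.6 has a chance Φ((3 − 2)/0.6) = Φ(1.67) = 95% of exceeding 2 points: *very likely*. At rho 0.5 the SE is 0.6 × 1.22 = 0.73, and Φ(1/0.73) is about 91%: *likely*.

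**The case against.** The strongest reply is that the documents do not show the limits to be wrong. At rho = 0 they are correct, and neither the sign nor the size of rho is given. Competitive play could even make opponents' efforts negatively related, which would make the limits conservative. This stands: a reader might infer that the limits are simply too narrow, and the documents do not support that. What remains is that the plan assumes rho = 0 in a game built so that each man responds to the other.

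Second, participant as the grouping unit is an inference. That stands too, but it is the only unit consistent with the aim of a within-participant SD.

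Third, the simulation is not this trial. Arm sizes, attendance, SDs and rho are assumed, the two venues ran at different times, and whether opponents were fixed or rotated is not stated. It is also unclear whether session number is a calendar slot or each man's own count, which would differ between opponents after absences. This weakens the exact session figures. It does not touch the 1 + rho result, which needs only a shared length.

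Fourth, the trial is exploratory and pairing alone has a modest effect. That limits the severity. However, the plan says that the intervals will inform future trials, so their calibration still matters.

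**Conclusion.** The concern holds in conditional form. The data are paired by design, the described model has no term for pair, bout or session, and the 90% limits and percent chances are calibrated only if the omitted dependence is absent.

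For duration, positive rho of 0.1 to 0.5 makes the true SE about 5% to 22% larger than reported and coverage about 88% to 82%; at rho = −0.3 coverage is about 95%. These figures rest on an assumed rho and a shared repetition length.

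For session, a reader might take pairing as the main cause. The calculations point elsewhere: missing participant-by-session variation or a missing random slope, each with an assumed SD of 2 points, takes coverage to about 70% or 64%, against about 85% for pairing at rho 0.3. Bias in the point estimates has not been shown. The change should be made, but it does not overturn the training-data analysis.

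**What to change.** 1. Name the grouping unit of the random intercept. State whether opponents were fixed or rotated, whether they shared each repetition length, and how session number was counted.
2. Keep the participant intercept and add a participant-by-session term and a random session slope.
3. Let the two opponents' residuals within a bout and repetition correlate with either sign, for example through a compound-symmetric or unstructured residual covariance for the pair, or report SEs clustered on bout. A bout random intercept alone is not enough, because its variance cannot be negative. Clustering on bout alone does not replace the random slope, which acts across a man's bouts. Records with no opponent in the trial enter as singletons.
4. Report whether any *likely*, *very likely* or *unclear* verdict changes.

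The cost is a few lines of model code and limits that may widen. It needs to be known who fought whom in each session. The documents say only that users' identifying information was entered, so this must be confirmed from session logs. If it cannot be recovered, the duration verdicts can still be shown with the SE multiplied by √(1 + rho) over a stated range of rho, and step 2 can still be done.
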